12.2 Flexible Sigmoidoscopy/Colonoscopy

To ensure quality data and standardization, the same endoscopist should be used throughout the trial wherever possible. Endoscopy images will be obtained during each endoscopy and will be sent for central reading and determination of the Mayo MES. A detailed image review charter from the central reading laboratory will outline the endoscopic procedures, video recordings and equipment. For each patient, video recording of the entire endoscopic procedure will be performed using an acceptable storage medium. The endoscopic recordings will be read centrally in a blinded manner for mucosal lesions and endoscopic severity by a qualified gastroenterologist according to the image review charter. The MES will be determined both at the Investigator site and centrally as described above. The complete and 9-point Mayo score used for clinical endpoints in the trial will utilize the MES derived from the central reader.

Biopsy

Each patient entered into the trial will have colonic biopsies obtained during flexible sigmoidoscopy/full colonoscopy as follows (see [Table 2](#)):

- One biopsy pair will be taken from the most inflamed area of the left colon. Biopsies will be placed in formalin. These biopsies will be analyzed centrally.
- ONLY if there is suspicion for clinically significant cytomegalovirus (CMV) colitis, one biopsy should be taken from the base of an ulcer to evaluate for histological presence of CMV, but otherwise is not necessary for inclusion in the trial. Analysis will be performed locally.
- Only if there is suspicion for dysplasia or malignancy, appropriate biopsies should be taken to exclude malignancy or assess dysplasia. Analysis should be performed locally.

Necrotic areas of ulcerated mucosa should be avoided during biopsy. The original location (colonic segment and endoscopic depth) of biopsy specimens should be clearly indicated.

In all cases, the video recordings are to be taken prior to biopsy and sent to central reading center of the study.

12.3 Patient-Reported Outcomes

Patient-reported outcomes (SFS and RBS components of the complete, 9-point, and partial Mayo score), and the clinician-reported PGA will be collected in an electronic diary. Patients will complete the SFS and RBS components of the Mayo subscore daily from the Baseline Visit until the [REDACTED] Visit.

Patients will be instructed on the use and completion of questions on the electronic diary. The patients' baseline SFS is to be recorded in RPC01-3102 using data collected on the first day of Screening from the RPC01-3101 or RPC01-202 trial. This is defined as the number of stools the patient passed in a 24-hour period prior to having UC or when the patient is in remission.

The diary entries will be reviewed by site personnel during screening (prior to dosing, if applicable) and during all trial visits, through the [REDACTED] Visit. The SFS and RBS diary entries 2 weeks prior to each trial visit will be used to calculate the complete, 9-point, and partial Mayo score.

Because the colonoscopy/flexible sigmoidoscopy preparations can interfere with the assessment of other clinical parameters, diary entries used to calculate the complete Mayo Score and Partial Mayo Score will not correspond to day(s) of bowel preparation or endoscopy.

13 ASSESSMENTS OF SAFETY

13.1 Safety Parameters

13.1.1 *Physical Examination*

A complete physical examination will include evaluation of the heart, lungs, head and neck, abdomen, skin, and extremities, as well as a check for visual symptoms. All significant findings that are present at the Baseline Visit must be reported on the relevant medical history/current medical conditions eCRF. A check for visual symptoms and a full examination of the skin should be repeated [REDACTED]. Significant findings made after Baseline that meet the definition of an AE must be recorded on the AEs eCRF.

At all other visits following the Baseline Visit (except [REDACTED] and 90-day SFU), an interim physical examination will be performed ([Table 2](#)). The interim physical examination will include body systems with previously noted abnormalities and/or those body systems associated with any new complaints from the patient.

13.1.2 *Height and Weight*

For all patients, height and weight will be measured at Visit [REDACTED] and at the [REDACTED] visit. Height and weight can also be measured at the SFU Visit at the discretion of the Investigator (eg, in the case of ongoing AEs that need to be further evaluated).

13.1.3 *Vital Signs*

Systolic and diastolic blood pressure and pulse will be assessed in a sitting position. An automated validated device may be used, if available. In case the cuff sizes available are not large enough for the patient's arm circumference, a sphygmomanometer with an appropriately sized cuff may be used.

[REDACTED]

13.1.4 *Electrocardiogram*

The 12-lead digital ECG devices will be provided to each clinical site by the central ECG laboratory for the duration of the trial. Detailed instructions describing the process for recording and transmission of the digital ECGs will be outlined in the trial-specific manual and provided to the site before the start of the trial. Paper versions of ECG tracings recorded at the times specified in the Schedule of Events ([Table 2](#)) will be printed and photocopied to preserve the ink if necessary, and kept at the site as source documentation.

An ECG will be performed while resting. Electrocardiograms will be performed [REDACTED]

[REDACTED] will be evaluated by the treating physician, with input if needed from a local cardiologist or a central reader to confirm if extended monitoring is required. Additional ECG monitoring will be performed on Days [REDACTED] if cardiac issues are identified on the prior day of dose escalation, as described in [Section 13.1.10](#).

Only clinically significant abnormalities should be reported in the medical history/current medical conditions or the AE eCRF. Clinically significant findings must be discussed with the Medical Monitor before enrolling the patient in the trial.

13.1.5 *Ophthalmological Examination*

[REDACTED] will be performed in patients with a history of uveitis or diabetes mellitus or underlying/coexisting retinal disease or in all patients if deemed necessary by local or national requirements, as scheduled in [Table 2](#). All original [REDACTED] images (colored printouts) are considered source documents that should be made available to the site upon request, or otherwise at the end of the study. [REDACTED]

[REDACTED] The [REDACTED] images may be reviewed by an independent panel of ophthalmologists assigned to this trial.

13.1.6 *Dermatological Examination*

Dermatological evaluations will be performed by the treating Investigator or designee as part of the physical exam, as scheduled in [Table 2](#). Patients with any suspicious finding noted during the examination will be referred to an appropriately qualified dermatologist for evaluation and treatment, if warranted.

[REDACTED]

13.1.8 *Monitoring of Adverse Events and Serious Adverse Events*

[figure not shown]
Throughout the course of the trial, every effort must be made to remain alert to possible AEs or SAEs. Refer to [Section 13.2](#) for definitions of AEs/SAEs, monitoring, and reporting. Refer to [Section 13.2.6](#) for AEs of special interest.

13.1.9 *Monitoring of Concomitant Therapy*

The use of concomitant medication and procedures will be monitored throughout the trial. Refer to [Section 10.5.2](#) for prohibited concomitant therapies.

13.1.10 *Guidelines for Cardiac Monitoring*

Patients entering the trial from the open-label period of RPC01-202 will continue to receive RPC1063 and no additional cardiac monitoring is required.

13.1.11 Clinical Laboratory Evaluations

The central laboratory will analyze the samples. Further details of the procedures to be followed for sample collection, storage, and shipment will be documented in a laboratory manual.

Additional and repeat laboratory safety testing may be performed at the discretion of the Investigator and analyzed by the local laboratory. Approval from the Medical Monitor must be obtained if any lab test is required to be repeated > 2 times.

- Hematology: Red blood cell count, total and differential WBC count (basophils, eosinophils, lymphocytes, monocytes, and neutrophils), platelet count, hemoglobin (Hb), hematocrit, mean corpuscular volume, mean corpuscular hemoglobin, and mean corpuscular hemoglobin concentration. Total WBC count and all differential WBC counts will not be disclosed for Visit █ only and will be monitored centrally throughout the trial.

- Chemistry:
 - Full chemistry panel at Baseline: sodium, potassium, chloride, calcium, magnesium, phosphate, blood urea nitrogen, glucose, HbA1c, albumin, alkaline phosphatase, creatinine, ALT, AST, gamma glutamyl transferase (GGT), total bilirubin, conjugated bilirubin, total cholesterol, triglycerides, high-density lipoprotein, low-density lipoprotein, and [REDACTED].
 - ◆ HbA1c will be repeated annually
 - All other visits – blood urea nitrogen, albumin, alkaline phosphatase, creatinine, ALT, AST, GGT, total bilirubin, conjugated bilirubin, [REDACTED]. Of note, [REDACTED] will not be disclosed for Visit [REDACTED] to maintain the blind from the parent trial from which a patient may be entering.
- Urinalysis: Leukocytes, specific gravity, bilirubin, blood, glucose, ketones, pH, protein, and urobilinogen
[REDACTED]
- The central laboratory will analyze routine [REDACTED]. Details regarding collection of samples, shipment of samples, reporting of results, laboratory reference ranges, and alerting abnormal values will be supplied to the site before site initiation in a trial laboratory manual. The results of the analysis will be made available to each site by the central laboratory.
- Investigators will be asked to comment on those abnormalities on the respective laboratory result page, including a notation of the clinical significance of each abnormal finding in the patient's source documents. The laboratory sheets will be filed with the patient's source documents.
- Pregnancy test: Serum β -hCG must be performed in females of childbearing potential at Baseline if more than 1 month has elapsed from the last pregnancy test in the parent trial. Urine

β -hCG will be performed in females of childbearing potential at each scheduled visit. Between scheduled visits up until the 90-day SFU Visit, monthly home urine pregnancy tests should be performed by the patient. If a urine pregnancy test result is positive, the Investigator will instruct the patient to suspend further RPC1063 dosing, if applicable, and schedule a follow-up appointment as soon as possible. A serum pregnancy test will be performed for confirmation, including after the 90-day SFU Visit, if needed.

13.2 Adverse Events and Serious Adverse Events

13.2.1 Definition of Adverse Events

An AE is any untoward medical occurrence in a patient or clinical investigation patient administered a pharmaceutical product, which does not necessarily have a causal relationship with this treatment. An AE can therefore be any unfavorable and unintended sign (including an abnormal laboratory finding), symptom, or disease temporally associated with the use of a medicinal product, whether or not considered related to the medicinal product (ICH E2A, II.A.1).

Ulcerative colitis disease relapse and related symptoms will be monitored as trial endpoints and thus will not be recorded as AEs, unless it qualifies as a serious AE to trigger safety reporting as described in [Section 13.2.5](#).

In cases of surgical or diagnostic procedures, the condition/illness leading to such a procedure is considered as the AE rather than the procedure itself.

An Adverse Drug Reaction (ADR) is defined as all noxious and unintended responses to a medicinal product causally related to any dose (ICH E2A, II.A.2).

An Unexpected ADR is defined as an adverse reaction, the nature of which is not consistent with the applicable product information (ICH E2A, II.A.3).

Each AE is to be evaluated for duration, severity, seriousness, and causal relationship to the investigational drug. The action taken and the outcome must also be recorded.

13.2.2 Definition of Serious Adverse Events

Definition of Serious Adverse Event (SAE): An SAE (experience) or reaction is any untoward medical occurrence that at any dose (ICH E2A, II.B):

- Results in death
- Is life-threatening

NOTE: The term life-threatening" in the definition of "serious" refers to an event in which the patient was at risk of death at the time of the event; it does not refer to an event which hypothetically might have caused death if it were more severe.

- Requires inpatient hospitalization or prolongation of existing hospitalization
- Results in persistent or significant disability/incapacity, or
- Is a congenital abnormality/birth defect

Medical and scientific judgment should be exercised in deciding whether expedited reporting is appropriate in other situations, such as important medical events that may not be immediately life-threatening or result in death or hospitalization but jeopardize the patient or may require

intervention to prevent one of the other outcomes listed in the definition above. *These should also usually be considered serious.*

Examples of such events may be related to CNS (Central Nervous System), cardiovascular, pulmonary, ophthalmic, gastrointestinal, genitourinary or other body systems and include events such as intensive treatment in an emergency room or at home for allergic bronchospasm; blood dyscrasias or convulsions that do not result in hospitalization; or development of drug dependency or drug abuse.

In case of a fatality, the cause of death is considered as the SAE, and the death is considered as its OUTCOME.

13.2.3 Assessment of Adverse Event Severity

The severity of the AE will be characterized as “mild, moderate, or severe” according to the following definitions:

- Mild events are usually transient and do not interfere with the patient’s daily activities.
- Moderate events introduce a low level of inconvenience or concern to the patient and may interfere with daily activities.
- Severe events are incapacitating and interrupt the patient’s usual daily activity.

13.2.4 Assessment of Adverse Event Relationship to Investigational Drug

The causal relationship between the investigational drug and the AE has to be characterized as unrelated, unlikely, possible, probable, or related. This medical assessment should be made as soon as feasible when reporting an SAE.

The Investigator is requested to assess the relationship of any AEs to treatment using the following definitions:

- Unrelated: Those AEs which are clearly and incontrovertibly due to extraneous causes (concurrent drugs, environment, etc.) and do not meet the criteria for drug relationship listed under Unlikely, Possible, Probable, or Related.
- Unlikely: An AE may be considered unlikely if it includes at least the first two features:
 - It does not follow a reasonable temporal sequence from administration of the drug
 - It could readily have been produced by the patient’s clinical state, environmental or toxic factors, or other modes of therapy administered to the patient
 - It does not follow a known pattern to the suspected drug
 - It does not reappear or worsen when the drug is re-administered
- Possible: an AE may be considered possible if it includes at least the first two features:
 - It follows a reasonable temporal sequence from administration of the drug
 - It could readily have been produced by the patient’s clinical state, environment or toxic factors, or other modes of therapy administered to the patient
 - It follows a known response pattern to the suspected drug

- Probable: an AE may be considered probable if it includes at least the first three features:
 - It follows a reasonable temporal sequence from administration of the drug
 - It could not be reasonably explained by the known characteristics of the patient's clinical state, environmental or toxic factors or other modes of therapy administered to the patient
 - It disappears or decreased on cessation or reduction in dose. There are exceptions when an AE does not disappear upon discontinuation of the drug (eg, bone marrow depression, fixed drug eruptions, tardive dyskinesia, etc.)
 - It follows a known pattern of response to the suspected drug
- Related: an AE may be considered related if it includes all of the following features:
 - It follows a reasonable temporal sequence from administration of the drug
 - It could not be reasonably explained by the known characteristics of the patient's clinical state, environmental or toxic factors or other modes of therapy administered to the patient
 - It disappears or decreased on cessation or reduction in dose. There are exceptions when an AE does not disappear upon discontinuation of the drug (eg, bone marrow depression, fixed drug eruptions, tardive dyskinesia, etc)
 - It follows a known pattern of response to the suspected drug
 - It reappears or worsens if the drug is re-administered

All efforts should be made to classify the AE according to the above categories.

After initiation of investigational drug, all AEs, regardless of relationship to investigational drug, will be recorded until the patient completes his or her last trial visit.

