7.3 Safety Endpoints

- The incidence, severity, and relationship of treatment-emergent adverse events (TEAEs), serious AEs (SAEs), TEAEs leading to discontinuation of investigational drug, AEs of special interest (AESIs), and TEAEs of special interest will be summarized.

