14.5 Safety Analyses

Adverse events will be monitored during the trial and the data analyzed with respect to incidence within each parent trial treatment group as well as severity and potential relationship of the AEs to investigational drug.

All AEs with a start date before the first dose date in RPC01-3102, which are ongoing from a previous trial to RPC01-3102, will be listed in the AE data listing and labeled as “Prior Adverse Event.”

Adverse events with an onset date on or after the first open-label dose date in RPC01-3102, or with onset prior to the first open-label dose date in RPC01-3102 that increase in severity on or after the first dose of investigational drug will be considered treatment emergent. Treatment-emergent AEs will be summarized for the Safety population by System Organ Class and Preferred Term and presented in descending order of frequency within each System Organ Class. Serious AEs and AEs leading to discontinuation will be summarized similarly.

Associated laboratory parameters such as hepatic profile, renal function, and hematology values will be grouped and presented together. For each laboratory test, individual patient values outside the standard reference range will be flagged and listed. Shift tables will be produced showing the frequency of shifts from Baseline to the highest and to the lowest on-trial value in and out of the normal range as well as by visit. Changes from Baseline to each visit for each numeric laboratory parameter will also be summarized.

The change from Baseline to each visit for each of the vital sign variables will be summarized. Abnormal vital sign values will be flagged and listed.

The change from Baseline to each visit for each of the ECG parameters will be summarized. An outlier analysis of ECG results will be conducted.

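### Section 13.2.4: the exclusion clause in Unrelated defeats that grade for the causes it names, so relationship summaries risk upward or inconsistent grading (minor)

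*Combined protocol and SAP*

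**What the plan says.** Section 13.2.4 requires each AE to be placed in one of five grades: unrelated, unlikely, possible, probable or related. Unrelated has two parts, joined by and. The AE must be among "Those AEs which are clearly and incontrovertibly due to extraneous causes (concurrent drugs, environment, etc", and it must be one of those that "do not meet the criteria for drug relationship listed under Unlikely, Possible, Probable, or Related".

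For Unlikely, the rule is "An AE may be considered unlikely if it includes at least the first two features". Those two are "It does not follow a reasonable temporal sequence from administration of the drug" and "It could readily have been produced by the patient’s clinical state, environmental or toxic factors, or other modes of therapy administered to the patient". Possible also needs only its first two features. The first is the negation of the timing feature under Unlikely. The second is the same alternative-cause feature, ending "environment or toxic factors, or other modes of therapy administered to the patient". The section sets no order of precedence among the grades, and it closes by asking that every effort be made to use these categories.

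The grade is used in three places. The safety endpoint in 7.3 is "The incidence, severity, and relationship of treatment-emergent adverse events (TEAEs") and related event classes. Section 14.5 analyses "severity and potential relationship of the AEs to investigational drug". Section 13.2.5 allows lighter supporting documentation for SAEs that are unrelated, so the protocol expects the grade to be assigned.

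**The concern.** The second part of the Unrelated definition appears to cancel the first. If an outside cause is certain, it is at least a ready explanation, and a ready explanation is what Unlikely and Possible ask for, whatever the timing. An investigator who follows the text step by step would then leave Unrelated unused for the causes it was written for. One who uses the word in its ordinary sense departs from the written rule. Both kinds of grading could end up in one table.

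Long-term safety is the first objective, and the trial has no control group (14.4), so the causality grade is one of the few attribution measures available. At stake are the split of TEAEs and SAEs by relationship and the documentation allowance in 13.2.5.

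**Working it through.** The plan gives no figure on this point, so the check is of the logic. All inputs come from the grade definitions in 13.2.4:

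- T: the temporal sequence from dosing is reasonable (a judgement).
- X: an alternative cause could readily explain the AE.
- N: no alternative cause reasonably explains it. X and N cannot both hold.
- D, K, R: improvement on stopping or reducing the drug, known pattern, recurrence on re-administration.
- E: the AE is clearly due to an extraneous cause.

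| Grade | Criteria as written |
|---|---|
| Unlikely | not T, and X |
| Possible | T and X |
| Probable | T, N and D |
| Related | T, N, D, K and R |
| Unrelated | E, and none of the four above |

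**Step 1.** Unlikely or Possible = (not T and X) or (T and X) = X. The two grades together take in every AE with a ready alternative cause, whatever its timing.

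**Step 2.** The causes named under Unrelated are concurrent drugs and environment. The alternative-cause feature names other therapy and environmental factors. An AE that is beyond dispute due to one of these could readily have been produced by it. For the named causes, E implies X.

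**Step 3.** With E true, X true and N false, the features T, D, K and R are free: 2 × 2 × 2 × 2 = 16 states. The 8 with T false meet Unlikely, the 8 with T true meet Possible, and 0 qualify as Unrelated.

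**Step 4.** Now drop the assumption that E implies X. The pair (X, N) has three allowed values, so there are 3 × 16 = 48 states with E true.

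- X true: 16 states, 8 Unlikely and 8 Possible.
- X false, N false: 16 states, none meeting another grade.
- X false, N true: 16 states, of which 4 (T and D true; K and R free) meet Probable and 12 meet no other grade.

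Unrelated is reachable in 16 + 12 = 28 of 48. All 28 have X false. They need an extraneous cause that is not clinical state, not environmental or toxic, and not another therapy. Only the open ending of the list of causes under Unrelated admits one.

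These are counts of logical states. They are not event frequencies.

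**The case against.** The strongest reply is that the grades are permissive and a matter of medical judgement, so an investigator may still choose Unrelated. That is right about practice, and the documents do not show that any AE has been misgraded. It does not rescue the text: the exclusion turns on whether an AE meets another grade's criteria, not on whether the investigator elects that grade.

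A second reply is that the clause means only that nothing points to the drug. That may be the intent. But the clause names Unlikely, and the features listed under Unlikely all point away from the drug, so this reading does not fit the words.

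A third reply is that the open list of causes leaves a route to Unrelated. It does, as Step 4 shows, and the point is therefore limited to causes covered by the alternative-cause feature. A definition that shuts out its own two examples is still defective.

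Three stronger inferences are tempting, and the documents support none of them.

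- *Plainly extraneous events are all graded possibly drug-related.* Those without a reasonable temporal sequence meet Unlikely. Nor does occurring during daily dosing settle the timing: for a fracture in a road accident, an investigator can reasonably find no sequence from dosing.
- *A known share of AEs is shifted.* The share moved to Possible is the fraction clearly extraneous, times the fraction of those judged to have reasonable timing, times the fraction graded literally. The documents give none of these. Assuming 10% to 50%, 50% to 100% and fully literal grading gives 0.10 × 0.50 = 5% to 0.50 × 1.00 = 50%, a range set only by the assumptions.
- *Drug-related incidence is inflated.* The visible text does not say how the five grades are pooled into related and not related.

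One point about cost also stands. First enrolment was estimated for August 2015 and this version is dated August 2022, about seven years later. A change without re-grading leaves grades assigned under two wordings.

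**Conclusion.** The wording is defective. Read literally, an AE clearly due to a concurrent drug or the environment cannot be graded Unrelated: it meets Possible or Unlikely according to the investigator's view of the timing. This rests on one assumption, that an established cause of either kind is also a ready alternative explanation, which is secure for the two named causes.

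The consequence is a risk of upward or inconsistent grading in the relationship summaries under 7.3 and 14.5, and of uneven use of the allowance for unrelated SAEs in 13.2.5. Its size cannot be quantified from the documents. Safety capture is unaffected: 13.2.4 records AEs whatever their relationship, and 13.2.5 requires SAEs within 90 days of the last dose to be reported whether or not they are thought related. The System Organ Class and Preferred Term tables in 14.5 are not described as filtered by relationship. Severity: minor.

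**What to change.** In 13.2.4, keep the first part of the Unrelated definition and replace the exclusion clause with a precedence rule: Unrelated is assessed first, and it applies when an extraneous cause is clearly and incontrovertibly established, regardless of timing. Add to Unlikely and to Possible that the AE does not meet Unrelated. The old clause should not stay beside these additions, because each definition would then depend on the other.

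Under this rule, the 16 states in Step 3 all become Unrelated. The 16 states with an alternative cause that is not clearly established (X true, E false) split into 8 Unlikely and 8 Possible, with no overlap among the three grades.

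In 14.5, tabulate the five grades separately, so that the affected boundaries stay visible whatever pooling is used. Give the date of the clarification in the study report.

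The cost is a short change to 13.2.4, a note to sites and a fuller relationship table. The small downside is that AEs graded earlier are not re-graded, so the summaries will span both wordings; the date and the separate grades let a reader allow for that.
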